#### 6.1.1.1 Dabrafenib (DRB436) and trametinib (TMT212) dosing

Study medications should be taken as follows:

- Dabrafenib will be administered twice daily per the dosing regimen shown in Table 6-1, Table 6-2, Table 6-3 and Table 6-4.
- Trametinib will be administered once daily per the dosing regimen shown in Table 6-5, Table 6-6, Table 6-7 and Table 6-8.
- Trametinib should be taken in combination with dabrafenib once daily, preferably in the morning.
- Dabrafenib capsules and trametinib tablets should be taken with approximately 120-240 mL of water.
- Trametinib pediatric oral solution formulation will be administered with a graduated syringe. Please refer to the trametinib oral solution Instructions for Use.
- Dabrafenib pediatric oral suspension formulation administration will be administered using dosing cup and/or graduated syringe. Please refer to dabrafenib oral suspension Instructions for Use.
- Refer to the dabrafenib and trametinib Instructions for Use documents if enteral feeding tubes are required for administering pediatric oral solutions.
- Patients less than 12 years of age who weigh less than 16 kg must be administered the dabrafenib dispersible tablets for oral suspension.
- Patients equal to or greater than 12 years of age who weigh less than 19 kg must be administered the dabrafenib dispersible tablets for oral suspension.
- Patients less than 6 years old who weigh less than 26 kg must be administered the trametinib oral solution.
- Patients older than 6 years old must weigh at least 33 kg to be administered the trametinib tablets.
- Patients should be encouraged to take dabrafenib at approximately 12 hour intervals and at similar times each day.
- Study treatment should be administered under fasting conditions, at least 1 hour before or 2 hours after a meal.
- If it is not possible for a patient to tolerate the fasting conditions noted above, study treatment may be administered with a small non-fat meal (e.g. small amount of apple juice/sauce, a piece of dry toast). Patients and their guardians should be advised to avoid administering study drug with milk or high-fat, high-calorie foods.
- Patients who are being breastfed may continue to be breastfed on demand. If the patient is breastfed during collection of PK samples the time of breastfeeding should be recorded as a meal.

- If a patient vomits after taking study drug, the patient should be instructed not to retake the dose and wait for the next scheduled dose.
- If a patient misses a dabrafenib dose, they should be instructed not to double the next regularly scheduled dose. However, patients may take the missed dose immediately if the next scheduled dose is at least 6 hours later. Patients may then take the next dose at the scheduled time.
- If a patient misses a trametinib dose, they should be instructed not to double the next regularly scheduled dose. However, patients may take the missed dose immediately if the next scheduled dose is at least 12 hours later. Patients may then take the next dose at the scheduled time.
- The total daily dose of dabrafenib will not exceed 300 mg (150 mg BID).
- The total daily dose of trametinib will not exceed 2 mg.

# 6.1.1.2 Additional dosing guidelines for pharmacokinetic sampling/chemistry panel collection

PK samples will be collected on all HGG patients and LGG patients randomized to receive dabrafenib with trametinib treatment. PK samples will not be collected from the LGG patients randomized to receive carboplatin with vincristine, even after crossover from carboplatin with vincristine to dabrafenib plus trametinib.

On days with PK, the following additional guidelines must be followed:

- On protocol visit days when PK blood collection is scheduled at the clinic, patients must take study treatment in the clinic under the supervision of the Investigator or designee. On all other days, patients may take dabrafenib and trametinib at home.
- Post-dose PK samples should be collected after dosing of the study treatment in the morning (AM). PK sample collection will be performed according to Table 7-5 and Table 7-6.

# 6.1.2 Carboplatin and Vincristine Dosing Regimen

Carboplatin and vincristine will be supplied locally as commercially available and labelled accordingly to comply with legal requirements of each country. Carboplatin and vincristine will be administered as one course of induction (10 weeks of chemotherapy with 2 weeks of rest), followed by 8 cycles of maintenance chemotherapy. Each maintenance cycle is 6 weeks. Maintenance cycles are only given following sufficient recovery of hematologic parameters.

Chemotherapy administration should follow the guidelines below and as per local product labels or SmPC. Please consult local product labels and institutional standards for duration of infusion and flush requirements when administering carboplatin and vincristine.

Local safety laboratory testing to confirm hematologic parameters may be conducted per institutional practice during induction and maintenance phases of chemotherapy prior to dosing when central labs are not scheduled per protocol or when central lab results will not be available prior to dosing. Results will be collected in the eCRF.

## 6.1.2.1 Induction Therapy

Prior to induction, central or local lab results must be assessed to confirm ANC  $\geq 1000/\mu L$  and platelet count  $\geq 100,000/\mu L$ .

Induction will consist of 10 weeks of therapy followed by 2 weeks without chemotherapy. Induction should only be interrupted in the event of grade 3 neurotoxicity, grade 2 nephrotoxicity, grade 4 hematologic toxicity, or disease progression. See Section 6.3.1.16 for dose modification guidelines.

Carboplatin (CBDCA): 175 mg/m^2 as weekly IV infusion over 60 minutes on weeks 1 to 4, and on weeks 7 to 10, on the same day as VCR dosing

Vincristine (VCR): 1.5 mg/m^2 as weekly IV bolus infusion (0.05 mg/kg if child is <12 kg) (maximum dose of 2.0 mg) for 10 weeks.

Table 6-9 Induction therapy

| Week
1 | Week
2 | Week
3 | Week
4 | Week
5 | Week
6 | Week
7 | Week
8 | Week
9 | Week
10 | Week
11 | Week
12 |
|-----------|-----------|-----------|-----------|-----------|-----------|-----------|-----------|-----------|------------|------------|------------|
| VCR        | Rest       | Rest       |
| CBDC      | CBDC      | CBDC      | CBDC      |           |           | CBD       | CBDC      | CBDC      | CBDC       |            |            |
| Α         | Α         | Α         | Α         |           |           | CA        | Α         | Α         | Α          |            |            |

## 6.1.2.2 Maintenance Therapy

Following induction therapy and two weeks of rest, maintenance therapy should begin if peripheral counts recover to ANC  $\geq 1,000/\mu L$  and platelet count  $\geq 100,000/\mu L$ . Repeat blood counts every 7 days until counts are adequate. Recovery of peripheral counts is required prior to starting each maintenance cycle. Local laboratory results may be used prior to dosing if a central lab is not scheduled per protocol or when central lab results will not available in time for a scheduled cycle. Results will be collected in the eCRF.

Each maintenance cycle will be 6 weeks in duration and consists of 4 weekly doses of carboplatin, and three weekly doses of vincristine given concomitantly with the first 3 weeks of carboplatin, followed by two weeks of rest. Maintenance will continue for a total of 8 cycles. See Section 6.3.1.16 for dose modification guidelines.

Carboplatin (CBDCA): 175 mg/m^2 as weekly IV infusion over 60 minutes on weeks 1 to 4 of each cycle.

Vincristine (VCR): 1.5 mg/m^2 as weekly IV bolus infusion (0.05 mg/kg if child is <12 kg) (maximum dose of 2.0 mg) on weeks 1 to 3 of each cycle, on the same day as CBDCA dosing.

Table 6-10 Maintenance therapy

| Week 1 | Week 2 | Week 3 | Week 4 | Week 5 | Week 6 |
|--------|--------|--------|--------|--------|--------|
| VCR    | VCR    | VCR    |        | Rest   | Rest   |
| CBDCA  | CBDCA  | CBDCA  | CBDCA  |        |        |

#### 6.1.3 Ancillary treatments

Not applicable

#### Protocol No. CDRB436G2201

#### 6.1.4 Rescue medication

Not applicable

#### 6.1.5 Guidelines for continuation of treatment

For guidelines for continuation of treatment, refer to Section 6.3.

#### 6.1.6 Treatment duration

#### Dabrafenib with trametinib:

Patients will receive dabrafenib in combination with trametinib until disease progression or loss of clinical benefit as determined by the investigator, death, unacceptable toxicity, withdrawal of consent or if the investigator judges that further therapy is no longer in the best interest of the patient, or early termination of the study by the sponsor.

Patients who have disease progression (as defined by RANO) may continue on study treatment if the investigator determines that the patient has clear evidence of clinical benefit from study treatment, continuing study drug may be in the best interest for the patient, and the patient/legal guardian is willing to continue on study drug and sign Informed Consent for treatment beyond progression. If the patient is continuing on study treatment, then all study procedures including tumor assessments must be followed as scheduled (Table 7-1 or Table 7-2). In addition, after each tumor assessment, the investigator must confirm and document in patient medical records and the eCRF that the patient is still benefitting from study treatment and therefore can continue receiving study treatment.

#### Carboplatin with vincristine for LGG Cohort only:

Duration of treatment should continue for the prescribed number of cycles, as tolerated or until unacceptable toxicity, start of a new anti-neoplastic therapy, discontinuation at the discretion of the investigator or patient/legal guardian, lost to follow-up, death, study is terminated by the sponsor or until disease progression.

Carboplatin should always be given in a setting with rapid access to pediatric advanced life-supporting support capability. See Section 6.3.1.16.5 for additional guidelines for the management of allergic reactions. Patients who develop an intolerable allergic reaction to carboplatin should be managed per institutional standards. Only after centrally confirmed RANO-defined disease progression will patients randomized to carboplatin with vincristine treatment will be allowed to crossover to receive dabrafenib in combination with trametinib treatment.

# 6.2 Dose escalation guidelines

Not applicable.

#### 6.3 Dose modifications

#### 6.3.1 Dose modification and dose delay

For patients who do not tolerate the protocol-specified dosing schedule, dosing interruptions or modifications are mandated in order to allow patients to continue the study treatment.

General guidelines regarding management and dose reduction for adverse events that are considered by the investigator to be related to study treatment and for which specific guidelines do not apply are provided in Table 6-11. These guidelines are intended primarily for toxicities not easily managed with routine supportive care. For example, alopecia is not an indication for dose modification, nor is grade 2 nausea and vomiting that can be easily managed with antiemetics. Refer to Section 6.3.1.16 for general guidelines for dose modifications for carboplatin and vincristine.

Table 6-11 General guidelines for dose modification for adverse events considered related to dabrafenib and trametinib combination treatment

| Grade                          | Recommended adverse event management guidelines  | Mandatory dose modification requirements   |
|--------------------------------|--|--|
| Grade 1 or Grade 2 tolerable   | 

Monitor closely.

Provide supportive care according
to institutional standards.

 | 
 
Continue dabrafenib and trametinib at
the same dose level.
 
   |
| Grade 2 intolerable or Grade 3 | 

Monitor closely.

Provide supportive care according to institutional standards.

     | 
 
Interrupt dabrafenib and trametinib
(except for cuSCC, keratoacanthoma,
new primary melanoma, and basal cell
carcinoma).
 
   |
|                                |  | 
 
When toxicity resolves to ≤ Grade
 
1 or baseline, restart dabrafenib
 
and trametinib reduced by one
 
dose level.
 
   |
|                                |  | 
 
If the Grade 2 (intolerable) or Grade 3
toxicity recurs, interrupt dabrafenib
and trametinib.
 
  |
|                                |  | 
 
When toxicity resolves to Grade 1
or baseline, restart dabrafenib
and trametinib reduced by
another dose level. Re-escalation
of the patient's dose is
recommended if criteria in
Section 6.3.1 are met.
 
 |
| Grade 4                        | 
 
Monitor closely.
 
   | 
 
Interrupt dabrafenib and trametinib.
 
   |
|                                | 
 
Provide supportive care according
to institutional standards.
 
                        | 
 
Restart with dabrafenib and trametinib
reduced by one dose level once
toxicity resolves to ≤ Grade 1 or
baseline or permanently discontinue
dabrafenib and trametinib at the
discretion of investigator.
 
     |

These are general guidelines and investigators should always use clinical judgment in adverse event management for any individual patient. Some toxicities may require hospitalization for stabilization, additional work-up, and consultation with a specialist before treatment can be restarted. Investigators should always err on the side of caution in these settings if treatment

related toxicity is a possibility. All dose modifications are based on the worst preceding toxicity using Common Terminology Criteria for Adverse Events (CTCAE) Version v4.03.

If treatment related toxicities occur that are specific to combination treatment of dabrafenib and trametinib, then both treatments should be simultaneously dose reduced, interrupted or discontinued with the exception shown below:

Exception where dose modifications are necessary for **only dabrafenib**:

- Uncomplicated pyrexia (Table 6-16)
- Uveitis (Table 6-21)

Exception where dose modifications are necessary for **only trametinib**:

- Retinal vein occlusions (RVO) (Table 6-19) and retinal pigment epithelial detachment (RPED) Table 6-20)
- Left ventricular ejection fraction (LVEF) reduction (Table 6-23)

If the patient requires a dose interruption of > 28 days (greater than 6 weeks for uveitis, iritis, see Table 6-21) from the previous dose for persistent grade 2 or greater dabrafenib and/or trametinib treatment related toxicity, then the patient must be discontinued from study treatment. Up to two dose reductions will be allowed.

Dose reductions will occur in increments of 50 mg from the total daily dose for dabrafenib capsules and in increments of 0.5 mg from the total daily dose for trametinib tablets. If a patient is receiving trametinib 0.05 mg/mL oral solution, dose modification guidelines in Table 6-12 and Table 6-13 should be followed. If patient is receiving dabrafenib dispersible tablet, dose modification guidelines in Table 6-14 and Table 6-15 should be followed. If more than two dose reductions are needed, the patient must be discontinued from study treatment. Patients who discontinue study treatment due to adverse event will be followed until resolution or stabilization of the event. All dose changes and the reason for dose interruption must be recorded on the Dosage Administration Record eCRF.

Table 6-12 Dose Modification for trametinib (TMT212) oral solution for patients greater or equal to 6 years old

| Weight (kg) | Dose |       | Dose Redu
Level 1 | ıction | Dose reduction
Level 2 |        |
|-------------|------|-------|----------------------|--------|---------------------------|--------|
|             | mL   | mg    | mL                   | mg     | mL                        | mg     |
| 10-12.5     | 5    | 0.25  | 3.5                  | 0.175  | 2.5                       | 0.1225 |
| 12.6-16.5   | 7.5  | 0.375 | 5                    | 0.25   | 3.5                       | 0.175  |
| 16.6-24.5   | 10   | 0.5   | 7                    | 0.35   | 5                         | 0.25   |
| 24.6-35     | 15   | 0.75  | 10                   | 0.5    | 7                         | 0.35   |
| 35.1-45     | 20   | 1.0   | 14                   | 0.7    | 10                        | 0.5    |
| 45.1-55     | 25   | 1.25  | 17.5                 | 0.875  | 12                        | 0.6    |
| 55.1-68     | 30   | 1.5   | 20                   | 1      | 14                        | 0.7    |
| 68.1-72     | 35   | 1.75  | 25                   | 1.25   | 17.5                      | 0.875  |
| >72         | 40   | 2     | 28                   | 1.4    | 20                        | 1      |

Dose: 0.025 mg/kg/day
Dose Level 1: ~30% reduction

Dose Level 2: ~30% reduction

| Weight
(kg) | Dose |       | Dose Re
Level 1 | eduction | Dose redu
Level 2 | ction  |
|----------------|------|-------|--------------------|----------|----------------------|--------|
|                | mL   | mg    | mL                 | mg       | mL                   | mg     |
| 7-9.9          | 5    | 0.25  | 3.5                | 0.175    | 2.5                  | 0.1225 |
| 10-12.5        | 7.5  | 0.375 | 5                  | 0.25     | 3.5                  | 0.175  |
| 12.6-16.5      | 10   | 0.5   | 7.5                | 0.375    | 5                    | 0.25   |
| 16.6-24.5      | 12.5 | 0.625 | 10                 | 0.5      | 7                    | 0.35   |
| 24.6-35        | 17.5 | 0.875 | 15                 | 0.75     | 10                   | 0.5    |
| 35.1-45        | 25   | 1.25  | 20                 | 1        | 14                   | 0.7    |
| 45.1-55        | 30   | 1.5   | 25                 | 1.25     | 17.5                 | 0.875  |
| ≥55.1          | 40   | 2     | 30                 | 1.5      | 20                   | 1      |

Dose: 0.032 mg/kg/day

Dose Level 1: ~0.025 mg/kg/day Dose Level 2: ~ 30% reduction

**Table 6-14** Dose Modification for dabrafenib (DRB436) dispersible tablet for patients less than 12 years of age

| Weight (kg) | Dose (b.i.d) | Dose Reduction Level 1 (b.i.d) | Dose Reduction Level 2 (b.i.d) |
|-------------|--------------|--------------------------------|--------------------------------|
| 7-9.5       | 20 mg        | 10 mg                          | 0 mg                           |
| 9.6-13.5    | 30 mg        | 20 mg                          | 10 mg                          |
| 13.6-17.5   | 40 mg        | 30 mg                          | 20 mg                          |
| 17.6-20.5   | 50 mg        | 40 mg                          | 30 mg                          |
| 20.6-24.5   | 60 mg        | 50 mg                          | 40 mg                          |
| 24.6-28.5   | 70 mg        | 60 mg                          | 50 mg                          |
| 28.6-32.5   | 80 mg        | 70 mg                          | 60 mg                          |
| 32.6-36.5   | 90 mg        | 80 mg                          | 70 mg                          |
| 36.6-40.5   | 100 mg       | 90 mg                          | 80 mg                          |
| 40.6-43.5   | 110 mg       | 100 mg                         | 90 mg                          |
| 43.6-47.5   | 120 mg       | 110 mg                         | 100 mg                         |
| 47.6-51.5   | 130 mg       | 120 mg                         | 110 mg                         |
| 51.6-55.5   | 140 mg       | 130 mg                         | 120 mg                         |
| ≥55.6 kg    | 150 mg       | 140 mg                         | 130 mg                         |

Dose: 5.25 mg/kg/day Dose level 1: 4.5 mg/kg/day Dose level 2: 3.75 mg/kg/day

**Table 6-15** Dose Modification for dabrafenib (DRB436) dispersible tablet for patients greater or equal 12 years of age

| Weight    | Dose (b.i.d) | Dose Reduction Level 1 (b.i.d) | Dose Reduction Level 2 (b.i.d) |
|-----------|--------------|--------------------------------|--------------------------------|
| 10-11.5   | 20 mg        | 10 mg                          | 0 mg                           |
| 11.6-17.5 | 30 mg        | 20 mg                          | 10 mg                          |
| 17.6-20.5 | 40 mg        | 30 mg                          | 20 mg                          |
| 20.6-24.5 | 50 mg        | 40 mg                          | 30 mg                          |

| 24.6-28.5 | 60 mg  | 50 mg  | 40 mg  |
|-----------|--------|--------|--------|
| 28.6-32.5 | 70 mg  | 60 mg  | 50 mg  |
| 32.6-36.5 | 80 mg  | 70 mg  | 50 mg  |
| 36.6-40.5 | 90 mg  | 80 mg  | 60 mg  |
| 40.6-43.5 | 100 mg | 90 mg  | 60 mg  |
| 43.6-47.5 | 110 mg | 100 mg | 70 mg  |
| 47.6-51.5 | 120 mg | 110 mg | 80 mg  |
| 51.6-55.5 | 130 mg | 120 mg | 80 mg  |
| 55.6-64.5 | 140 mg | 130 mg | 100 mg |
| ≥64.6     | 150 mg | 140 mg | 110 mg |
|           |        |        |        |

Dose: 4.5 mg/kg/day
Dose level 1: 3.75 mg/kg/day
Dose level 2: 3.00 mg/kg/day

If a patient's dose of dabrafenib and trametinib has been reduced per the dose modification instructions, dose re-escalation may be considered provided the following criteria are met:

- A period of 4 weeks of treatment have passed since restarting dosing at the lower dose level and treatment has been well tolerated
- Patient is deriving clinical benefit

Dose re-escalation follows the same dosing steps as de-escalation, in increments of 50 mg from the total daily dose for dabrafenib capsules and in increments of 0.5 mg from the total daily dose for trametinib tablets. Patients receiving trametinib 0.05 mg/mL oral solution are to follow Table 6-12 and Table 6-13 for dose re-escalation. Patients receiving dabrafenib dispersible tablet are to follow Table 6-14 and Table 6-15 for dose re-escalation. The dabrafenib dose must not exceed 150 mg twice daily (300 mg total daily dose). The trametinib dose must not exceed 2 mg once daily.

The following sections address the specific instructions for mandatory dose modifications and recommended management for AEs considered suspected to be related to study treatment.

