#### 6.3.1.1 Pyrexia

Episodes of pyrexia syndrome have been observed in patients receiving dabrafenib monotherapy or in combination with trametinib. The pyrexia syndrome is defined as treatment-related fever (≥38°C) or chills/rigors/night sweats or flu-like symptoms. In a minority of cases pyrexia was accompanied by symptoms such as severe chills/rigors, dehydration, and hypotension, dizziness or weakness and required hospitalization. The incidence and severity of pyrexia syndrome are increased when dabrafenib is used in combination with trametinib compared to dabrafenib monotherapy.

Patients and guardians must be instructed on the importance of immediately reporting febrile episodes. Dabrafenib and trametinib must be interrupted promptly and anti-pyretics (acetominophen, ibuprofen, similar) started at the very first symptom of pyrexia or its associated prodrome (chills or rigors or night sweats or flu-like symptoms). Adequate hydration status should be maintained. Dabrafenib and trametinib should be restarted upon improvement of symptoms of at least 24 hours, and at the same dose.

In the event of recurring pyrexia events despite the use of antipyretics and drug interruption, the use of oral corticosteroids may be considered when restarting dabrafenib and trametinib. In patients experiencing pyrexia associated with rigors, severe chills, dehydration or hypotension, serum creatinine increase and other evidence of renal function decrease should be monitored carefully during and following severe events of pyrexia.

Pyrexia accompanied by hypotension, dehydration requiring intravenous fluids, renal insufficiency and/or severe (≥ Grade 3) rigors/chills in the absence of an obvious infectious cause are to be reported as a SAE.

Guidelines for dose modification and management for pyrexia syndrome considered to be related to dabrafenib are provided in Table 6-16.

Table 6-16 Mandatory dose modification and recommended clinical management for pyrexia syndrome suspected to be related to dabrafenib and/or trametinib treatment

| Pyrexia   |   |   |  |
|---|---|---|--|
| Occurrence  | Recommended adverse event management guidelines   | Mandatory dose modification requirements  |  |

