| 1 st occurrence and
subsequent
occurrence s | 
 
Re-educate patient/family about pyrexia syndrome and immediately interrupt dabrafenib and trametinib at the very first symptom of pyrexia or its associated prodrome (chills or rigors or night sweats or flu-like symptoms).
 
Clinical evaluation for infection and hypersensitivitya
 
Laboratory work-upa
 
Administer anti-pyretic treatment with nonsteroidal anti-inflammatory drugs (NSAID) and/or paracetamolb
 
Oral hydration should be encouraged in patients without evidence of dehydration. Intravenous hydration is recommended in patients experiencing pyrexia complicated by dehydration/hypotension.
 
For recurring pyrexia events despite the use of anti-pyretics and dose interruption, consider oral corticosteroids (i.e. prednisone 10mg or pediatric equivalent, or more) for at least 5 days or as clinically indicated.
 
Optimize oral corticosteroid dose as clinically indicated for recalcitrant pyrexia
 
 | Dabrafenib and trametinib must be interrupted promptly at the very first symptom of pyrexia or its associated prodrome (chills, rigors, night sweats or flu-like symptoms) Adequate hydration status should be maintained. Dabrafenib and trametinib should be restarted upon improvement of symptoms of at least 24 hours, at the same dose     If pyrexia cannot be managed with interruption, dose reduction must be considered if clinically indicated. |  |

- a. For patients experiencing pyrexia, a clinical evaluation and laboratory work-up is mandatory for each event; thorough clinical examination for signs and symptoms of infection or hypersensitivity is required; laboratory work-up should include full-blood-count, electrolytes, creatinine, blood urea nitrogen (BUN), Creactive protein (CRP), liver transaminases, blood culture, and urine culture.
- b. Anti- pyretic treatment should be started immediately at the first occurrence and prophylactic anti-pyretic treatment is recommended. Anti-pyretic treatment may include acetaminophen, ibuprofen, or suitable anti-pyretic medication according to institutional standards. Prophylactic anti-pyretic treatment is recommended to be discontinued after three days in the absence of pyrexia.

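### Two of the four single-drug exceptions in Protocol Section 6.3.1 misstate the tables they cite: pyrexia entirely, LVEF reduction for symptomatic patients

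*Protocol*

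**What the plan says.** Protocol Section 6.3.1 sets a general rule for treatment-related toxicities that are specific to the combination: "then both treatments should be simultaneously dose reduced, interrupted or discontinued with the exception shown below". Four bullets follow. Two are dabrafenib-only: "Uncomplicated pyrexia (Table 6-16") and uveitis, citing Table 6-21. Two are trametinib-only: retinal vein occlusion with retinal pigment epithelial detachment (RVO/RPED), citing Tables 6-19 and 6-20, and "Left ventricular ejection fraction (LVEF) reduction (Table 6-23").

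Section 6.3.1.1 says of pyrexia: "Dabrafenib and trametinib must be interrupted promptly and anti-pyretics (acetominophen, ibuprofen, similar) started at the very first symptom of pyrexia". The mandatory column of Table 6-16, in a single row covering first and later occurrences, says: "Dabrafenib and trametinib must be interrupted promptly at the very first symptom of pyrexia or its associated prodrome". Both places restart both drugs at the same dose after at least 24 hours of improvement. The last step in that cell is: "If pyrexia cannot be managed with interruption, dose reduction must be considered if clinically indicated".

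Table 6-23 has two rows. In asymptomatic LVEF decrease, trametinib is interrupted and dabrafenib stays at its current dose. In symptomatic decrease, trametinib is stopped permanently, and dabrafenib is interrupted and restarted only once LVEF and symptoms have recovered.

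On precedence, the opening of Section 6.3.1 confines Table 6-11 to events without specific guidelines. The section closes with: "The following sections address the specific instructions for mandatory dose modifications and recommended management for AEs".

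**The concern.** The list reads as a summary of the tables it names. In two places the summary and the table give different instructions for the same child. A site acting on the list could leave a febrile child on trametinib, or a child with symptomatic LVEF decrease on dabrafenib. In both cases the mandatory column of the cited table requires that drug to be interrupted.

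Section 12 permits no authorized deviations and has significant ones reported in the CSR, so whichever text a site follows, it departs from the other. Section 10.3 summarizes dose adjustments for the individual drugs separately. Those summaries would therefore depend on which text sites followed: for trametinib in pyrexia, and for dabrafenib in symptomatic LVEF decrease.

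**Working it through.** No formula applies. The check sets each bullet against the mandatory column of its cited table.

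| Bullet in Section 6.3.1 | List says | Cited table says | Result |
|---|---|---|---|
| Uncomplicated pyrexia | dabrafenib only | Table 6-16: both drugs interrupted and restarted, all occurrences | conflict |
| Uveitis | dabrafenib only | Table 6-21: dabrafenib interrupted, trametinib continued | agrees |
| RVO/RPED | trametinib only | Tables 6-19 and 6-20: trametinib interrupted or stopped, no dabrafenib change required | agrees |
| LVEF reduction | trametinib only | Table 6-23, asymptomatic: dabrafenib dose unchanged | agrees |
| LVEF reduction | trametinib only | Table 6-23, symptomatic: dabrafenib interrupted as well | conflict |

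Result: 2 of 4 bullets conflict with their table, pyrexia in full and LVEF in 1 of 2 rows.

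**Could the word uncomplicated rescue the pyrexia bullet?** It could if Table 6-16 or Section 6.3.1.1 had a separate branch for uncomplicated episodes. Neither has one: complications change hydration and monitoring, not which drugs are interrupted. The protocol does not define uncomplicated pyrexia either. Section 6.3.1.1 does say "In a minority of cases pyrexia was accompanied by symptoms such as severe chills/rigors, dehydration, and hypotension", so on an ordinary reading the bullet covers the usual presentation. That is an inference.

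**Does other text settle the conflict?** The introductory sentence in Section 6.3.1 subordinates Table 6-11 to specific guidelines, but names only that table. The closing sentence points sites to the specific sections without saying what happens when the list disagrees with them. Section 6.3.1 also tells investigators to err on the side of caution, which favours the tables but is not a precedence rule.

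**How often would it matter?** Section 1.2.3 calls pyrexia the most common AE of the combination. Section 1.2.3.1 reports, among 12 children on the combination, pyrexia in 58% regardless of cause, and ejection fraction decrease as a possibly related SAE in two (17%). These are not rates of uncomplicated treatment-related pyrexia or of symptomatic LVEF decrease, so no patient count can be derived.

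**The case against.** The strongest reply is that the bullets are pointers. Each names its table, and a site that opens the table finds the stricter instruction in the mandatory column. The general-guideline language, the sentence leading into the specific sections and the advice to be cautious all lean towards the specific text. Harm needs a site to act on the list without opening the table, and nothing shows that this has happened. This stands as a reason to grade the point modestly. It does not make the bullets correct, because the one sentence that subordinates general guidance does not mention the list.

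Three stronger readings are tempting but not supported.

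- A reader might infer that the list is also wrong because it omits other single-drug rules, such as those for pneumonitis, pancreatitis and venous thromboembolism. The general rule covers only toxicities specific to the combination, so the list need not be exhaustive, and those events have explicit instructions of their own. The omissions are not contradictions.
- A reader might infer that, with the pyrexia bullet gone, the general rule would reduce both drugs when interruption fails. That is not established. Section 6.3.1.1 reports pyrexia syndrome with dabrafenib alone as well as with the combination, so it is not clearly a combination-specific toxicity. The reduction step in Table 6-16 is discretionary and names no drug, although the sentences before it in the same cell name both.
- A reader might infer that sites need an immediate notice. The cited tables already carry the stricter rule, so the next amendment is soon enough.

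**Conclusion.** The point holds for two bullets. The pyrexia bullet contradicts Section 6.3.1.1 and Table 6-16 for every episode it could cover. The LVEF bullet is too broad: right for asymptomatic decrease, wrong for symptomatic decrease. The other two bullets are sound.

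This is an internal inconsistency in a paediatric dosing instruction and should be fixed. Its reach is patient safety and the per-drug dose-adjustment summaries. ORR, power and type I error are unaffected. The conclusion assumes that the tables state the sponsor's intent, which is reasonable because Section 6.3.1.1 repeats the Table 6-16 rule and both tables carry the mandatory column.

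**What to change.** At the next amendment:

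1. Delete the pyrexia bullet from the dabrafenib-only list.
2. Change the LVEF bullet to: Asymptomatic LVEF reduction (Table 6-23).
3. Add one sentence to Section 6.3.1: where an event-specific section or table exists, it governs over the general rule and over this list.
4. Optionally, state in Table 6-16 which drug or drugs are reduced if interruption does not control pyrexia. This is a clinical decision for the sponsor.

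The cost is two bullet edits and one sentence, plus one clause if item 4 is taken up. Data collection, analysis and sample size do not change.
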